# **1.6 Definition of Cardiovascular Death**

Cardiovascular death includes sudden cardiac death, death due to acute myocardial infarction, death due to heart failure, death due to stroke, and death due to other cardiovascular causes, as follows:

- 1. **Sudden Cardiac Death**: refers to death that occurs unexpectedly in a previously stable patient and includes the following deaths:
  - (a) Witnessed and instantaneous without new or worsening symptoms
  - (b) Witnessed within 60 minutes of the onset of new or worsening cardiac symptoms
  - (c) Witnessed and attributed to an identified arrhythmia (eg, captured on an electrocardiographic (ECG) recording or witnessed on a monitor by either a medic or paramedic)
  - (d) Patients unsuccessfully resuscitated from cardiac arrest or successfully resuscitated from cardiac arrest but who die within 24 hours without identification of a non-cardiac etiology
  - (e) Unwitnessed death or other causes of death (information regarding the patient's clinical status within the week preceding death should be provided)
- 2. **Death due to Acute Myocardial Infarction**: Death occurring up to 14 days after a documented acute myocardial infarction [verified either by the diagnostic criteria outlined for acute myocardial infarction or by autopsy findings showing recent myocardial infarction or recent coronary thrombus] and where there is no conclusive evidence of another cause of death.

If death occurs before biochemical confirmation of myocardial necrosis can be obtained, adjudication should be based on clinical presentation and ECG evidence.

Death due to a myocardial infarction that occurs as a direct consequence of a cardiovascular investigation/procedure/operation will be classified as death due to other cardiovascular cause.

- 3. **Death due to Heart Failure or Cardiogenic Shock**: refers to death occurring in the context of clinically worsening symptoms and/or signs of heart failure without evidence of another cause of death. New or worsening signs and/or symptoms of congestive heart failure (CHF) include any of the following:
  - (a) New or increasing symptoms and/or signs of heart failure requiring the initiation of, or an increase in, treatment directed at heart failure or occurring in a patient already receiving maximal therapy for heart failure.

- (b) Heart failure symptoms or signs requiring continuous intravenous therapy or oxygen administration
- (c) Confinement to bed predominantly due to heart failure symptoms
- (d) Pulmonary oedema sufficient to cause tachypnea and distress not occurring in the context of an acute myocardial infarction or as the consequence of an arrhythmia occurring in the absence of worsening heart failure
- (e) Cardiogenic shock not occurring in the context of an acute myocardial infarction or as the consequence of an arrhythmia occurring in the absence of worsening heart failure.

Cardiogenic shock is defined as systolic blood pressure (SBP) < 90 mm Hg for greater than 1 hour, not responsive to fluid resuscitation and/or heart rate correction, and felt to be secondary to cardiac dysfunction and associated with at least one of the following signs of hypoperfusion:

- Cool, clammy skin *or*
- Oliguria (urine output < 30 mL/hour) *or*
- Altered sensorium *or*
- Cardiac index  $< 2.2 \text{ L/min/m}^2$

Cardiogenic shock can also be defined as  $SBP \ge 90 \text{ mm Hg}$  as a result of positive inotropic or vasopressor agents alone and/or with mechanical support in less than 1 hour.

The outcome of cardiogenic shock will be based on CEC assessment and must occur after randomisation. Episodes of cardiogenic shock occurring before and continuing after randomisation will not be part of the study endpoint.

This category will include sudden death occurring during an admission for worsening heart failure.

4. **Death due to Cerebrovascular Event** (intracranial hemorrhage or nonhemorrhagic stroke): refers to death occurring up to 30 days after a suspected stroke based on clinical signs and symptoms as well as neuroimaging and/or autopsy, and where there is no conclusive evidence of another cause of death.

Definition of Death due to Stroke: refers to death occurring up to 30 days after a stroke that is either due to the stroke or caused by a complication of the stroke.

5. **Death due to Other Cardiovascular Causes**: death must be due to a fully documented cardiovascular cause not included in the above categories (eg, dysrhythmia, pulmonary embolism, or cardiovascular intervention).

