## 12.2.4 Interim analyses

When 50% of the total number of events has been accrued (ie, at 520 events), an interim analysis for superiority only will be performed. The analysis will test for superiority at the 1-sided 0.15% level (p<0.0015) (Lan-deMets [O'Brien-Fleming] spending function, East 5.2, Copyright © 2008 Cytel Inc.), the sequential testing methodology specified for the final analysis will be used, although the study will not be stopped for non-inferiority at the interim

unless superiority is also shown. The 1-sided alpha level used for the final analyses will be 0.0245.

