# **12.3** Determination of sample size

Assuming a 2.1% annual event rate on placebo, an approximately 15 months - accrual period, with an approximate 3-year additional follow-up period, a 17% reduction of risk in the saxagliptin group and a 2.8% rate of annual study discontinuation, randomising 16500 patients is expected to yield 1040 primary endpoint events, which would provide 85% power to test for superiority of saxagliptin versus placebo at the 2.45% 1-sided level. This number of events will also provide at least 98% power to test the following hypothesis at the 2.45% 1-sided level:

H01: HR [saxagliptin:placebo]  $\geq$ 1.30

VS

H11: HR [saxagliptin:placebo] <1.30.

**The original event rate was based on the following assumptions**: A 2.5% annual event rate for patients without moderate to severe renal impairment is assumed based upon CV event rates observed in previous studies conducted in patients with T2DM. With an assumed 5% annual event rate in the patients with moderate renal impairment, and an assumed 10% annual event rate in patients with severe renal impairment, the overall annual event rate in the study population is estimated to be 2.8%. **Based on the current observed event rate, the assumed overall event rate will be 1.8%**.

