# **1.1 Myocardial Infarctions**

All myocardial infarctions (MIs) will be counted as events whether they represent the reason for the hospitalisation or occurred during a hospitalisation. In addition, they will be counted as events whether they occurred spontaneously or as the direct consequences of an investigation/procedure or operation. In order to meet the criteria as an endpoint, an MI must be distinct from the qualifying event (ie, re-infarction for a patient who qualified for the study based on recent MI). The definition of MI as an endpoint will take into account whether a patient had a recent MI or has undergone revascularisation with percutaneous coronary invention (PCI) or coronary artery bypass graft (CABG) surgery. In cases where both cardiac troponin and CK-MB are available (drawn at similar time points) and are discordant, biomarker criteria will be applied using cardiac troponin. The definitions of MI are as follows for the 4 clinical settings in which it may occur:

A. **Spontaneous MI (normal biomarkers)** - For patients with no recent revascularisation in whom biomarkers were never elevated or have been documented to return to normal after a qualifying (or recent) MI, criteria 1 and 2 or criterion 3 or criterion 4 must be met:

- 1. Typical cardiac biomarker rise and/or fall with the following degrees of elevation accepted as biochemical evidence of myocardial necrosis (either one or both):
  - Troponin T or I: maximal concentration greater than the MI decision limit
  - CK-MB: maximal concentration greater than the ULN

AND

- 2. At least 1 of the following additional supportive criteria:
  - (a) Ischaemic discomfort at rest lasting >10 minutes or
  - (b) ECG changes indicative of ischaemia (ST elevation > 0.1 mV or ST depression > 0.05 mV, or new T-wave inversions)

OR

3. Development of new, abnormal Q waves (>30 msec in duration and >1 mm in depth) in >2 contiguous precordial leads or >2 adjacent limb leads; or increase R amplitude in V1-V3 consistent with posterior infarction

OR

4. Pathologic findings of an acute MI.

B. **Spontaneous MI (Elevated biomarkers)** - For patients with no recent revascularisation in whom biomarkers from a qualifying (or recent) MI remain elevated, criteria 1 and 2, or criterion 3, or criterion 4 must be met:

1. Cardiac biomarker re-elevation defined as:

- (a) Increase by at least 20% of the previous value; and

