### AND

- 2. At least one of the following supportive criteria:
  - (a) Development of new, abnormal Q waves (>30 msec in duration and >1 mm in depth) in >2 contiguous precordial leads or >2 adjacent limb leads; or increase R amplitude in V1-V3 consistent with posterior infarction, or
  - (b) Angiographically documented new graft or native coronary occlusion, or
  - (c) Imaging evidence of new loss of viable myocardium

OR

3. Pathologic findings of an acute MI.

Note: symptoms are not required.

Note: If cardiac troponin measurements are the only cardiac biomarker data available, they may be used by the Clinical Event Adjudication Committee (CEC), along with the ECG and clinical scenario, in the adjudication of suspected MI after revascularisation (PCI or CABG).

The reviewers should also consider the clinical features (eg, renal insufficiency), possible alternative diagnoses (eg, pericarditis), pattern of marker release (eg, absence of a rise and/or fall), and known sensitivity/specificity of the various cardiac markers in the adjudication of infarction, particularly when there is discordance in the results of multiple markers.

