# **1.7 Definition of Non-Cardiovascular Death**

Non-cardiovascular death is defined as any death not covered by cardiac death or vascular death and is categorised as follows:

- Pulmonary causes
- Renal causes
- Gastrointestinal causes
- Infection (includes sepsis)
- Non-infectious (eg, systemic inflammatory response syndrome (SIRS))
- Malignancy (ie, new malignancy, worsening of prior malignancy)
- Hemorrhage, not intracranial
- Accidental/Trauma
- Suicide
- Non-cardiovascular system organ failure (eg, hepatic failure)
- Non-cardiovascular surgery

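### Two rules in Appendix G for primary endpoint events need correcting: sudden cardiac death item 1(e) can take in deaths of known non-cardiovascular cause, and the marker rules for MI after PCI or CABG contradict each other.

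*Protocol*

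**What the plan says.** Protocol section 12.1.3 refers the definition of all primary and secondary efficacy endpoint events to Appendix G. Sections 12.2.2 and 12.2.3 use the events confirmed by the adjudication committee (CEC) for both the 1.30 safety test and the superiority test.

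**Deaths.** Appendix G section 1.6, item 1, defines sudden cardiac death as unexpected death in a previously stable patient and lists five forms. The fifth, (e), is "Unwitnessed death or other causes of death", and it asks only for information on the patient's status in the week before death. Section 1.7 then states: "Non-cardiovascular death is defined as any death not covered by cardiac death or vascular death". Its list includes accident or trauma, suicide, and haemorrhage other than intracranial. Section 1.8 counts deaths attributed to neither class as presumed cardiovascular.

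**MI.** The opening paragraph of section 1.1 says that when troponin and CK-MB are both available and "are discordant, biomarker criteria will be applied using cardiac troponin". It then introduces four clinical settings and exempts none of them. Setting C (within 24 hours after PCI) and setting D (within 24 hours after CABG) give thresholds for CK-MB only. A note after setting D begins: "If cardiac troponin measurements are the only cardiac biomarker data available, they may be used by the Clinical Event Adjudication Committee (CEC". The paragraph after that note asks reviewers to weigh the clinical features and marker properties, especially when several markers disagree.

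**The concern.** These are stated rules for the trial's only primary endpoint, and applying them as written can give a wrong or irreproducible call.

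For deaths, the second half of item 1(e) has no boundary beyond the opening condition of item 1. Because section 1.7 is residual, the cardiovascular categories are applied first, and a death that fits 1(e) never reaches the non-cardiovascular list. Events that the drug does not influence would then enter the composite. They would bring the hazard ratio nearer to 1, which weakens the superiority test and is anti-conservative for the test against 1.30.

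For MI after a procedure, three instructions apply to the same case and do not agree. Two adjudicators who both follow the text could reach opposite decisions.

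**Working it through.** **1. Deaths: exclusion of another cause, by category in section 1.6**

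| Category | Safeguard against another cause |
|---|---|
| 1(d), cardiac arrest | No non-cardiac aetiology identified |
| 1(e) | None |
| 2, acute MI | No conclusive evidence of another cause |
| 3, heart failure or shock | No evidence of another cause |
| 4, cerebrovascular | No conclusive evidence of another cause |
| 5, other cardiovascular | Cardiovascular cause must be fully documented |

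Deaths of undetermined cause already count as cardiovascular under 1.8. The first half of 1(e), on unwitnessed death, therefore changes little. The second half can only add deaths whose cause is known and lies elsewhere.

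**2. The plan's own figures**

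Inputs, all from the protocol:
- Final one-sided level (12.2.4): "The 1-sided alpha level used for the final analyses will be 0.0245". This gives z = 1.969.
- Effect (12.3): "a 17% reduction of risk in the saxagliptin group", so the hazard ratio is 0.83.
- Events (12.3): 1040, stated to give "85% power to test for superiority of saxagliptin versus placebo at the 2.45% 1-sided level" and at least 98% power against the 1.30 margin.
- Allocation (3.1): 1:1.

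Schoenfeld approximation, with √(1040/4) = 16.12:
- Superiority power = Φ(16.12 × |ln 0.83| − 1.969) = Φ(1.036) = 85.0%.
- Non-inferiority power at a true ratio of 1 = Φ(16.12 × ln 1.30 − 1.969) = Φ(2.262) = 98.8%.

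Both agree with the plan.

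**3. Illustration of dilution from item 1(e)**

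Let f be the share of placebo-arm primary events that are miscounted deaths unaffected by drug. The documents give no value for f, so 2% and 5% are assumptions. The diluted ratio is (1 − f) × HR + f, and the total is held at 1040 events.

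| f | True 0.83 becomes | Superiority power | True 1.30 becomes | Chance of passing the 1.30 test |
|---|---|---|---|---|
| 0 | 0.830 | 85.0% | 1.300 | 2.45% |
| 2% | 0.833 | 83.4% | 1.294 | 2.9% |
| 5% | 0.839 | 80.8% | 1.285 | 3.7% |

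The last column is Φ(16.12 × ln(1.30 / diluted ratio) − 1.969). For f = 5% this is Φ(16.12 × 0.0116 − 1.969) = Φ(−1.78) = 3.7%.

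If the miscounted deaths came on top of 1040 drug-sensitive events instead (1040/0.95 = 1095 in total at f = 5%), superiority power would be 82.8%.

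**4. MI after PCI or CABG, both markers available and discordant**

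| Instruction in section 1.1 | Troponin raised, CK-MB below its limit | CK-MB above its limit, troponin not raised |
|---|---|---|
| Opening paragraph | Points to MI, but C and D have no troponin limit to apply | Points to no MI |
| Settings C and D | Marker criterion not met | Marker criterion met |
| Note after D | Troponin not admitted, since it is not the only marker | Same |
| Closing paragraph | Reviewer judgement | Reviewer judgement |

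In setting D the marker must be joined by supporting evidence, so fewer calls depend on it alone. The first kind of discordance adds an MI if the opening paragraph is followed; the second removes one. No arithmetic on the hazard ratio is possible from this.

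**The case against.** On deaths, the context argues against the literal reading. Item 1(e) stands under a heading about sudden cardiac death and applies only to unexpected deaths in stable patients. Section 1.7 names accident, suicide and non-intracranial bleeding as non-cardiovascular, and a sensible committee would not code a documented suicide as cardiac. Adjudication is independent and blinded (12.4.1), uses death certificates and autopsy reports (6.1), and follows a manual that is not shown. This stands as a limit on the size. It does not make the text right, because correct results then depend on reviewers setting the written rule aside. All-cause mortality, the next secondary endpoint, does not depend on cause of death and offers a partial check.

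The documents also give a rough sense of scale. The pooled phase IIb/III data in section 1.1.3.3 report 10 + 12 = 22 deaths, of which 7 + 10 = 17 were cardiovascular, beside 41 primary MACE. Counting all five remaining deaths as events would give at most 5/46, about 11%. The numbers are small and the population differs. Only unexpected deaths in stable patients could be affected, so the real share should be well below that.

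On MI, the closing paragraph of section 1.1 does address discordance, and settings C and D can be read as specific rules that override the general one. That is a possible reconciliation, but the text does not state it.

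A reader might infer that the marker conflict also adds drug-unrelated events and dilutes the hazard ratio. The documents do not support this. The conflict can add or remove MIs, and nothing shows that post-procedure MI is unaffected by treatment. Hospitalisation for coronary revascularisation is itself a component of the first secondary endpoint (12.1.3.2).

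**Conclusion.** Both wording errors are present and should be corrected.

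Item 1(e) conflicts with section 1.7 and lacks the exclusion that neighbouring categories carry. Its consequence is conditional: the hazard ratio moves toward 1 only if such deaths are actually counted, the drug does not affect them, and the true ratio differs from 1. The share is unknown and probably small. The 2% and 5% rows show sensitivity and are not estimates. The effect on the 1.30 test deserves most attention, because blinding keeps misclassification even between arms but does not remove the dilution.

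The marker rules for settings C and D contradict the opening paragraph of section 1.1 and leave discordant cases open to either call. The fault is lack of reproducibility; the direction and size of any effect on event counts or on the hazard ratio are undetermined.

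A reader might infer that the primary result is materially biased. The documents do not establish that.

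**What to change.** **Section 1.6, item 1(e).** Delete the second half of the phrase (everything after the word 'or') and limit the item to unwitnessed deaths with no identified non-cardiovascular cause. Section 1.7 then governs identified non-cardiovascular causes, and 1.8 continues to cover undetermined deaths.

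**Section 1.1.** Reconcile the opening paragraph, settings C and D, the note and the closing paragraph into one marker hierarchy for MI after PCI or CABG. Exempting C and D from the troponin rule would do this, and so would giving them a troponin criterion. The documents do not favour either, so the choice belongs to the CEC and the study leadership. State also where reviewer judgement enters.

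**Cost.** An amendment of a few sentences to Appendix G, the matching text in the CEC manual, and blinded re-review of events already adjudicated under the affected wording. Sample size, alpha and analysis model do not change.

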# **1.7 Definition of Non-Cardiovascular Death**

Non-cardiovascular death is defined as any death not covered by cardiac death or vascular death and is categorised as follows:

- Pulmonary causes
- Renal causes
- Gastrointestinal causes
- Infection (includes sepsis)
- Non-infectious (eg, systemic inflammatory response syndrome (SIRS))
- Malignancy (ie, new malignancy, worsening of prior malignancy)
- Hemorrhage, not intracranial
- Accidental/Trauma
- Suicide
- Non-cardiovascular system organ failure (eg, hepatic failure)
- Non-cardiovascular surgery

# **1.8 Definition of Presumed Cardiovascular Death**

Presumed Cardiovascular Death: All deaths not attributed to the categories of cardiovascular death and not attributed to a non-cardiovascular cause, are presumed cardiovascular deaths and as such are part of the cardiovascular mortality endpoint.

# 1. BACKGROUND AND RATIONALE

Circulating biomarkers have proven to play a pivotal role in the evaluation and treatment of patients who are at risk of developing or have established atherosclerotic vascular disease, and their full potential has likely yet to be realized. Like atherosclerosis, diabetes is also considered a chronic inflammatory disease with activation of multiple pathologic inflammatory, thrombotic, and metabolic pathways (Pradhan et al 2002). Patients with elevated levels of circulating pro-inflammatory and thrombotic biomarkers are at a particularly high risk of developing incident diabetes (Meigs et al 2004, Festa et al 2006), however, data regarding the risk associated with elevated levels of biomarkers, alone and in combinations, in patients with established diabetes is remarkably scarce.

Biomarkers may be used to facilitate diagnosis, enhance risk assessment, direct therapeutic decision-making, and monitor therapy (Morrow et al 2007). In particular, there is proof of principle that the combined use of multiple biomarkers that reflect distinct pathobiological contributors to atherothrombotic risk enhances assessment of prognosis. (Sabatine et al 2002). There is a need for prospective evaluation of established and novel biomarkers, both alone and in a multimarker strategy, in a broader population of patients with diabetes either with established atherosclerotic vascular disease or with multiple risk factors.

New insight into the pathobiology of the causes and consequences of atherothrombosis and diabetes has fostered a steady pace of emergence of candidate novel cardiovascular and metabolic biomarkers. Using novel markers that reflect the inflammatory, thrombotic, metabolic, and haemodynamic mediators of risk in patients with diabetes and atherosclerotic disease, it may be possible to characterise non-invasively the participation of these different pathobiological contributors in an individual patient and to monitor response to therapy (Morrow et al 2003).

For example, high-sensitivity testing for C-reactive protein (hs-CRP) has emerged as a convenient tool for detecting low-level systemic inflammation that portends a higher risk of a first myocardial infarction or stroke, as well as poor short-term and long-term prognosis (Ridker et al 1997). BNP and NT-proBNP have now been also shown to act as robust predictors of the short-term and long-term risk of cardiovascular death across the spectrum of acute coronary syndromes, as well as in patients with stable ischaemic heart disease or in the general population (Kragelund et al 2005, Morrow et al 2005, Zethelius et al 2008). Other novel biomarkers that are associated with prognosis in patients with atherothrombosis include soluble CD40 ligand (a marker of platelet activation), metalloproteinases (enzymes that disrupt the integrity of the atheroma's protective cap), myeloperoxidase (a potential participant in oxidative injury during atherogenesis) and vascular growth factors such as placental growth factor. In addition, improvements in technology have allowed for the measurement of earlier upstream precursors that may enable the identification of novel markers and the earlier detection of ischaemia, before myonecrosis. Proteomic and metabolomic techniques have been explored for this purpose (Sabatine et al 2005, Lewis et al 2008, Gerszten et al 2009).

It has become increasingly recognized that many of the pathobiological processes underlying acute and chronic atherosclerotic disease are present in patients with diabetes as well. These shared pathological mechanisms, including inflammation (Schillinger et al 2003) and procoagulant properties (Santilli et al 2006), provide insights into the increased cardiovascular risk associated with diabetes as well as the severity of diabetes itself (Pradhan et al 2002, Ndumele et al 2006, Katakami et al 2007).

Specific markers reflecting the vascular effects associated with glucose and lipid dysregulation have also been proposed with specific focus on patients with diabetes. For example, circulating advanced glycation products (AGEs), the soluble receptor for these AGEs (sRAGE), as well plasma phospholipid levels and ratios have been proposed as prognostic markers for vascular disease and heart failure (Katakami et al 2006, Guo et al 2008, Koyama et al 2008).

While a significant proportion of the existing research has explored biomarkers in the setting of diagnosis and risk stratification, it has been recognised that in some cases they may be active components or closely related to the pathobiological mechanisms underlying acute coronary syndrome and as such may be useful in assessing adequacy of therapy or even as therapeutic targets.

Several pharmacologic therapies have been shown to modify biomarkers and therefore offer insight into their potential mechanism of benefit. Statins as well as other lipid-lowering therapies, for example, have been shown to reduce markers of inflammation, such as CRP. Patients who achieved the greatest reduction in CRP with statin therapy were less likely to have recurrent atherothrombotic events (Ridker et al 2005, Morrow et al 2006).

In terms of antidiabetic agents, thiazolidinedione have the most compelling data regarding reduction in inflammatory makers. Multiple small studies lasting weeks or months have shown that rosiglitazone and pioglitazone reduce levels of CRP compared to placebo or sulphonylureas in patients with and without diabetes (Haffner et al 2002, Hetzel et al 2005, Forst et al 2007, Hanefeld et al 2007). There is little data regarding the effect of insulin or metformin on inflammatory markers in patients with diabetes. One small study of poorly controlled diabetic patients found a reduction in CRP in patients treated with insulin, but not sulphonylureas. (Yudkin et al 2000). Another study of 22 patients found treatment with metformin reduced levels of CRP by 33% at 4 months when it was added to sulphpfonylureas (Chu et al 2002).

There are few reports regarding the effect of incretin therapy on inflammatory models, however, animal studies have suggested that glucagon-like-peptide-1 (GLP-1) agonist may improve myocardial function (Fields et al 2009, Timmers et al 2009). The evaluation of cardiovascular biomarkers in patients treated with saxagliptin, which will increase levels of GLP-1, may provide important insight into the pathology of diabetic cardiovascular disease.

This study presents a unique opportunity to study the performance of a broad array of established and novel biomarkers in a diabetic population with established cardiovascular

disease or multiple risk factors in terms of response to therapy with saxagliptin and overall association with clinical outcomes.

